#### **5.7.1.1. Supportive Analysis**

The following two supportive primary endpoint analyses will be performed:

- WOMAC pain subscale scores averaged across Weeks 4, 8, and 12.
- WOMAC pain subscale scores averaged across Weeks 8 and 12.

The same method as for the primary endpoint will be used for handling missing data

Similarly, all supportive analyses described in Section 4.4.2.1 will be analyzed in a similar manner as the primary endpoint.

### **5.7.1.2. Subgroup Analysis**

Descriptive analyses are to be performed on the primary endpoint and secondary endpoints of physical function subscale score and PGA to summarize the treatment effects across subpopulations defined by:

- K-L category [2-3, or 4]
- Geographical region [USA, MGU (Republic of Moldova, Georgia, Ukraine), Poland]
- Age group [< 65, >= 65]
- Sex [Male, Female]
- Weight group [< median baseline weight, ≥ median baseline weight kg]
- BMI group [≤ median baseline BMI, > median baseline BMI]
- Duration of OA (DOA) at baseline [≤ median baseline DOA, > median baseline DOA]

Forest plots for the subgroup analysis are to be provided for all above subgroups for the primary endpoint. Summaries and plots by visit are to be provided for the primary endpoint and secondary endpoints of physical function subscale score and PGA by K-L category and geographic region.

### **5.7.2. Analysis of Secondary and Exploratory Efficacy Variables**

Analyses of continuous variables in secondary (Section 4.4.2) and exploratory (Section 4.4.3) endpoints are to use the same analysis method as the primary efficacy variables.

Analysis of categorical variables in secondary endpoints (Section 4.4.2) is to use the Cochran-Mantel-Haenszel approach stratified by the K-L category (2-3 vs 4 for index knee at screening) with missing data considered as non-response.

Exploratory endpoints for MOTICON (Section 4.9) will be addressed in a separate SAP.

Plots of mean values and change from baseline in PGA, WOMAC subscale and total score by Visit: Least Squares Mean (+/- SE) will be presented.

Cumulative distribution of percent change from baseline to Week 12 in the WOMAC pain and physical function scores will be presented by treatment group. The cumulative distribution plot displays a continuous plot of the percent change from baseline on the X-axis and the percent of patients experiencing that change on the Y-axis.

### **5.7.3. Adjustment for Multiple Comparison**

Control for multiplicity for both the primary and key secondary efficacy analyses is described in Section 5.7.1.

## 5.8. Analysis of Safety Data

The analysis of safety and tolerability is to be performed on the SAF, as defined in Section 3.2.

The safety analysis is to be based on the reported AEs and other safety information (clinical laboratory evaluations, vital signs, 12-lead ECG, Physical Examination, etc.) and is to be summarized by treatment group.

Treatment-Emergent Potential Clinically Significant Values (PCSV) in laboratory variables, vital signs and ECG are defined in Appendix 11.2.

The summary of safety results will be presented for each treatment group and by visit where applicable.

**Study observation period:** The observation period is divided into the four segments defined in Section 5.

### 5.8.1. Adverse Events

The verbatim text, the preferred term, and the primary SOC are to be listed in patient listings. Summaries that include frequencies and proportions of patients reporting AEs are to include the preferred terms and the SOCs.

**Pre-treatment AEs** are defined as AEs that developed or worsened during the Pre-Treatment Period.

**Treatment-emergent AEs (TEAEs)** are defined as AEs that developed or worsened during the Treatment Periods.

**Follow-Up AEs** are defined as AEs that developed or worsened after treatment period end (more than 4 weeks after the last dose of study drug) but before Week 36 visit.

The focus of adverse event reporting in the clinical study report is on TEAEs.

Summaries of TEAEs by treatment group, summarizing number (percentage) of patients within the specified category, during the study and by study period as applicable include:

- Overview of TEAEs, summarizing number of events,
  - Total number of TEAEs
  - Total number of Serious TEAEs
  - Patients with any TEAEs
  - Patients with any Serious TEAEs
  - Patients with any TEAEs leading to death
  - Patients with any TEAEs leading to withdrawal from study
  - Patients with any TEAEs leading to permanent study treatment discontinuation
- All TEAEs by SOC and PT
- All TEAEs by SOC, PT, severity

- All TEAEs by SOC, PT, relationship
- Study drug related TEAEs by SOC and PT
- TEAEs resulting in permanent study drug discontinuation by SOC and PT
- TEAEs leading to study drug infusion interruption by SOC and PT
- Serious TEAEs by SOC and PT
- All AEs by SOC and PT
- All AEs by severity
- All SAEs, by study period
- All SAEs by severity and study period
- All SAEs by relationship, treatment and follow-up period

Follow-up AEs will be summarized similarly as TEAEs, as well as AEs occurring during Treatment and Follow-up Periods combined.

Listing to include:

- Listing of AEs leading to death
- Listing of TEAEs leading to permanent study treatment discontinuation
- Listing of TEAEs leading to infusion interruption
- Listing of TEAEs leading to withdrawal from study
- Listing of patients with Serious TEAEs
- Listing of all joint replacements

Counts are to be provided according to treatment group and combined REGN5069 group for each PT within each primary SOC. Percentages are to be calculated based on the SAF in each treatment group and sorted by descending order of frequency of system organ class for the REGN5069 1000 mg group.

Within each primary SOC, PTs are to be sorted by decreasing frequency in the REGN5069 1000 mg group. For tables presenting severity of events, the worst severity is to be chosen for patients with multiple instances of the same event.

Counts of each PT in decreasing order of frequency are to also be provided. TEAEs with preferred terms  $\geq 5\%$  in any treatment group are to be summarized in the report.

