### 2.2. Sample Size and Power Considerations

Up to approximately 240 patients (80 per treatment group) are randomized to 3 treatment groups in a 1:1:1 allocation. Assuming a standard deviation (SD) of 2.3, 80 patients per treatment group provides approximately 80% power to detect a treatment difference of 1.1 between the REGN5069 dose and the matching placebo in change from baseline to week 12 in Western Ontario and McMaster Universities Osteoarthritis Index (WOMAC) pain subscale score (using a significance level of 0.05, 2-sided t-test and assuming a dropout rate of 15% [6% due to lack of efficacy or AEs, and 9% due to other reasons]).

[figure not shown]
The WOMAC index is comprised of 24 parameters grouped in subscales (pain, physical function, stiffness) and is reported using a Numerical Rating Scale score of 1-10.

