#### **3.2. The Safety Analysis Set (SAF)**

The safety analysis set (SAF) includes all randomized patients who received any study drug and is based on the treatment received (as treated). Treatment compliance/administration and all safety variables are analyzed using the SAF.

Determination of "as treated" is done as follows:

- Patients randomized to the placebo arm who receive at least one dose of active REGN5069 1000mg will be considered as treated with REGN5069 1000mg.
- Patients randomized to the placebo arm who receive at least one dose of active REGN5069 100mg and no dose of REGN5069 1000mg will be considered as treated with REGN5069 100mg.
- Patients randomized to any of the REGN5069 arms that did not receive any dose of either REGN5069 1000mg or 100mg will be considered as treated with placebo and classified in the placebo treatment arm for the purpose of analysis using the SAF.

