## 5. STATISTICAL METHODS

For continuous variables, descriptive statistics include the following: the number of patients reflected in the calculation (n), mean, median, standard deviation (SD), minimum, maximum, and the first and third quartiles (Q1 and Q3).

For categorical or ordinal data, frequencies and percentages are displayed for each category.

Unless otherwise specified, table content is to be presented sorted by descending order of frequency of system organ class for the REGN5069 1000 mg group.

**Study Observation Period** – Unless otherwise stated, analysis of all safety and non-safety variables captured at multiple visits are to be analyzed by the following observations periods:

- *The Pre-Treatment Period* is defined as the time from signing the ICF to before the first dose of study drug.
- *The Treatment Period* is defined as the days from first dose of study drug to the day of last dose + 28 days (4 weeks). Summaries for the Treatment Period are based on the SAF.
- *The Follow-Up Period* is defined from the end of the Treatment Period to the Week 36 Visit/Early Termination Visit, regardless of the patient having completed the treatment period (week 12 visit) or not.
- *The Post-Follow-Up Period* is defined from the end of the Follow-Up Period to the phone call/Early Termination Visit.

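### Follow-Up AE percentages are divided by the whole Safety Analysis Set, including patients who left before follow-up began, and no at-risk number or exposure-adjusted rate is planned

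*SAP*

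**What the plan says.** SAP 5.8 sets the population for all safety output: "The analysis of safety and tolerability is to be performed on the SAF, as defined in Section 3.2". Membership is broad: "The safety analysis set (SAF) includes all randomized patients who received any study drug" (SAP 3.2). Reaching follow-up is not a condition.

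SAP 5.8.1 gives the denominator for AE tables, "Percentages are to be calculated based on the SAF in each treatment group", and extends the table set beyond the Treatment Period: "Follow-up AEs will be summarized similarly as TEAEs, as well as AEs occurring during Treatment and Follow-up Periods combined". It names no separate denominator for the Follow-Up tables.

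Follow-Up AEs are "AEs that developed or worsened after treatment period end (more than 4 weeks after the last dose of study drug) but before Week 36 visit" (SAP 5.8.1). According to SAP 5, follow-up opens once treatment-period observation closes and lasts until the week-36 or early termination visit, and this applies "regardless of the patient having completed the treatment period (week 12 visit) or not". Its start is therefore specific to each patient: last dose + 28 days.

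The only dropout figure in either document is the planning value in Protocol 10.2 and SAP 2.2, where power for the week-12 comparison is stated "assuming a dropout rate of 15" per cent (6% for lack of efficacy or AEs, 9% for other reasons).

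**The concern.** A patient whose last contact falls within 28 days of the last infusion contributes nothing to routine AE observation in the Follow-Up Period, yet is counted as someone who was watched there and had no event. The percentage is then too low as an estimate of incidence among patients actually followed.

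Observed time also varies among those who do enter. A patient who stops after one infusion but stays in the study enters follow-up early and is watched for longer than one who received all three. A plain percentage cannot show this, and no rate per unit of time is specified for AEs.

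This matters because Protocol 3.2.1 justifies the 24-week follow-up as a precaution against late harm, citing experience with anti-NGF agents. SAP 4.5.2 lists TEAE incidence over the whole study as a secondary safety endpoint, but SAP 5.8.1 confines TEAEs to the Treatment Period. AE incidence after treatment therefore rests on the Follow-Up and combined-period tables. The Follow-Up summary was added in SAP Version 2.0 (SAP 1.2.4.2, Table 2), so it is a current, intended output.

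**Working it through.** **Inputs.** 80 patients per arm, difference 1.1, SD 2.3, two-sided 0.05 and 15% dropout (SAP 2.2). Infusions on days 1, 29 and 57; week 36 is day 253 (SAP 11.1, Table 3).

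**Step 1: the plan's own figure.** Evaluable per arm = 80 × (1 − 0.15) = 68. Normal-approximation power = Φ(1.1 / (2.3 × √(2/68)) − 1.96) = 79.6%; the noncentral t gives 79.1%. This reproduces the stated 80%. With all 80 per arm, power would be 85.7% (85.2% by t), so the 15% is built into the sample size.

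**Step 2: dilution.** Let f be the share of those dropouts who leave the study before their own last dose + 28 days. The documents do not give f, so it is an assumption here.

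Patients per arm who never enter follow-up = 80 × 0.15 × f.
Reported % / % among patients who entered = 1 − 0.15 × f.

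| f | Never enter, per arm | Number entering | Relative understatement |
|---|---|---|---|
| 0.25 | 3 | 77 | 3.8% |
| 0.50 | 6 | 74 | 7.5% |
| 0.75 | 9 | 71 | 11.3% |
| 1.00 | 12 | 68 | 15.0% |

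**Step 3: in percentage points.** At the ceiling (f = 1):

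- 4 patients with an event: 4/80 = 5.0% against 4/68 = 5.9% (0.9 points)
- 8 patients: 10.0% against 11.8% (1.8 points)
- 16 patients: 20.0% against 23.5% (3.5 points)

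At f = 0.5, 8 patients give 10.0% against 8/74 = 10.8%.

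**Step 4: between arms.** With equal true risk, the reported ratio is (1 − early loss in one arm) / (1 − early loss in the other). Equal loss gives 1, so there is no distortion. As an assumed illustration only, 20% against 10% gives 0.80/0.90 = 0.89, which makes the arm with more early loss look safer.

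**Step 5: length of follow-up to day 253, doses on schedule.**

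- Three infusions: last dose day 57, follow-up days 86 to 253 = 168 days (24 weeks)
- One infusion, patient stays in the study: last dose day 1, follow-up days 30 to 253 = 224 days (32 weeks)

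**Step 6: does another output repair it?** SAP 5.6.1 tabulates observation time, but from the first dose, so it does not give the number at risk after each patient's last dose + 28 days. SAP 5.5 reports completion of weeks 12 and 36, not entry to follow-up. The rule in SAP 6 that leaves patients with missing data out of percentages yields where something else is specified, and SAP 5.8.1 specifies the SAF.

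**The case against.** Several objections carry weight.

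- **The 15% is a ceiling.** It is a sample-size assumption for the week-12 endpoint, and reaching the ceiling needs every dropout to leave within 28 days of the last dose. Patients who stop drug are asked to stay for all remaining visits, and those who withdraw before week 12 are asked back at week 12 (Protocol 7.3.2 and 8.1.3; SAP 5.5). A return on day 85 would give 56 days of follow-up after one infusion (days 30 to 85) and 28 days after two (days 58 to 85). The likely figure is below 15%.
- **Early leavers can still contribute SAEs.** A reader might infer that they can have no Follow-Up AE at all. That is wrong: SAEs with onset up to 226 days after the last dose are reportable for early terminators if the investigator learns of them (Protocol 9.4.2; SAP 4.5.1), and the Follow-Up AE definition turns on onset date. What they lack is routine AE collection.
- **Joint harm has its own analysis.** SAP 4.6 and 5.8.8 cover adjudicated arthropathy and joint replacement, with Kaplan-Meier analysis if the data allow. Censoring handles unequal follow-up there. The point therefore concerns the general AE tables.
- **An at-risk denominator conditions on remaining in the study**, which happens after randomization. This is true, and it is a reason to allow the SAF percentage alongside.
- **The stakes are modest.** The report focuses on TEAEs, Protocol 10.3.2 puts safety on the SAF, and development in this indication has stopped.

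A reader might also carry the week-12 dropout hazard forward to week 36 and infer a much larger understatement. The documents give no dropout figure after week 12, and lost person-time is not a bias in a percentage of patients.

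These points limit the size of the problem. They do not make patients without observation a proper part of the denominator.

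**Conclusion.** The point holds in a limited form. SAP 5.8.1 divides Follow-Up AE counts by all treated patients, including those who left before follow-up began, and gives neither the number at risk nor a rate that allows for unequal follow-up.

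The dilution equals the share of treated patients who never enter follow-up. It is at most 15% in relative terms if the plan's dropout assumption applies and every dropout leaves within 28 days of the last dose, and 7.5% if half do. The true split is not in the documents. Comparison between arms is affected only if early loss differs by arm, and nothing in the documents shows that it does.

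This is worth correcting because follow-up was designed as a safety period and the correction is cheap. It does not undermine the TEAE tables, the combined-period tables or the adjudicated imaging analysis.

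**What to change.** In SAP 5.8.1, for the Follow-Up AE tables:

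1. Print, by arm, the number of SAF patients with any observed time after last dose + 28 days.
2. Base the Follow-Up percentage on that number. The SAF percentage may be shown beside it.
3. Add patients with an event per patient-year of observed follow-up. Time runs to the last contact at which AEs were collected, up to week 36, and includes the visits after joint replacement (SAP 11.1, Table 4).
4. List separately any SAE reported under the 226-day rule in a patient outside that number, so that it is neither lost nor counted without its denominator.
5. Keep the SAF for TEAE tables and for the combined Treatment and Follow-up tables.

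The cost is SAP wording and reprogrammed Follow-Up tables, using dates already collected. The downsides are two Ns in the AE section and an at-risk N that conditions on staying in the study; a footnote should state both.

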### **5.8.2. Clinical Laboratory Measurements**

Laboratory test results are to be summarized by baseline and change from baseline to each scheduled assessment time with descriptive statistics based on the SAF by treatment group and combined REGN5069 group for Treatment Period and Follow-Up Period.

Listings are to be provided with flags indicating the out of laboratory range values.

A Treatment-emergent Potential Clinically Significant abnormal value (PCSV) is a laboratory value that was normal at Screening and Baseline but became abnormal and met PCSV criteria after treatment with study drug. Definition of PCSV is listed in Appendix 11.2. Treatment-emergent Potentially clinically significant values (PCSVs) are to be summarized based on the SAF by treatment group and combined REGN5069 group, as well as presented in a listing.

For Alkaline phosphatase, hemoglobin, WBC, ALT, AST, creatinine, potassium, bilirubin, plots of means of the observed values by visit are to be presented by treatment group. For all analytes, plots of change from baseline by visit are to be presented by treatment group.

For hs-CRP, plots of medians of the observed values and change from baseline over time are to be presented by treatment group.

If it is decided that CTX-1, P1NP, Osteocalcin, C1M, and C3M are to be measured and analyzed, the analyses will be made under a separate SAP.

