##### Laboratory Tests

Laboratory test results will be summarized by baseline and change from baseline to each scheduled assessment time with descriptive statistics.

Number and percentage of patients with a PCSV at any post-randomization time point will be summarized for each clinical laboratory test.

Shift tables based on baseline normal/abnormal and other tabular and graphical methods may be used to present the results for laboratory tests of interest.

Listings will be provided with flags indicating the out-of-laboratory range values.

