***Handling of Potentially Clinically Significant Values/Abnormalities (PCSA/PCSVs)***

If patients have a missing baseline value, they are grouped in the category “normal/missing at baseline”.

For PCSAs with 2 conditions, one based on a change from baseline value and the other on a threshold value or a normal range, with the first condition being missing, the PCSA is based only on the second condition.

For a PCSA defined on a threshold and/or a normal range, this PCSA is derived using this threshold if the normal range is missing; eg, for eosinophils the PCSA is  $>0.5$  GIGA/L or  $>\text{ULN}$  if  $\text{ULN} \geq 0.5$  GIGA/L. When ULN is missing, the value 0.5 should be used.

Measurements flagged as invalid by the laboratory are not be summarized or considered in the computation of PCSA values.

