WBC	<3.0 Giga/L and >=3.0 Giga/L at baseline (Non-Black); <2.0 Giga/L and >=2.0 Giga/L at baseline (Black) ≥16.0 Giga/L and < 16 Giga/L at baseline	Increase in WBC: not relevant.  To be interpreted only if no differential count available.
Lymphocytes	>4.0 Giga/L and <= 4.0 Giga/L at baseline	
Neutrophils	<1.5 Giga/L and >=1.5 Giga/L at baseline (Non-Black); <1.0 Giga/L and >=1.0 Giga/L at baseline (Black)	International Consensus meeting on drug-induced blood cytopenias, 1991. FDA criteria.
Monocytes	>0.7 Giga/L <= 0.7 Giga/L at baseline	
Basophils	>0.1 Giga/L <= 0.1 Giga/L at baseline	
Eosinophils	(>0.5 Giga/L and >ULN) and (<=0.5 Giga/L or <= ULN at baseline)	Harrison - Principles of internal Medicine 17 th Ed., 2008.
Hemoglobin	≤115 g/L and > 115 g/L at baseline for male; ≤95 g/L and > 95 g/L at baseline for Female. ≥185 g/L and <185 g/L at baseline for Male; ≥165 g/L and < 165 g/L at baseline for Female  Decrease from Baseline ≥20 g/L	Three criteria are independent.  Criteria based upon decrease from baseline are more relevant than based on absolute value. Other categories for decrease from baseline can be used (≥30 g/L, ≥40 g/L, ≥50 g/L).
Hematocrit	≤0.37 v/v and > 0.37 v/v at baseline for Male ; ≤0.32 v/v and > 0.32 v/v at baseline for Female  ≥0.55 v/v and < 0.55 v/v at baseline for Male ; ≥0.5 v/v and < 0.5 v/v at baseline for Female	Two Criteria are independent

Parameter	Treatment-Emergent PCSV	Comments
RBC	Female $<3$ Tera/L and baseline $\geq 3$ Tera/L $\geq 6$ Tera/L and baseline $< 6$ Tera/L Male $<4$ Tera/L and baseline $\geq 4$ Tera/L $\geq 7$ Tera/L and baseline $< 7$ Tera/L	Unless specifically required for particular drug development, the analysis is redundant with that of Hb. Otherwise, consider FDA criteria.
Platelets	$<100$ Giga/L and $\geq 100$ Giga/L at baseline $\geq 700$ Giga/L and $< 700$ Giga/L at baseline	International Consensus meeting on drug-induced blood cytopenias, 1991. Two independent criteria
Urinalysis		
pH	$\leq 4.6$ and $> 4.6$ at baseline $\geq 8$ and $< 8$ at baseline	Two independent criteria
Vital signs		
HR	$\leq 50$ bpm and decrease from baseline $\geq 20$ bpm $\geq 120$ bpm and increase from baseline $\geq 20$ bpm	To be applied for all positions (including missing) except STANDING.
SBP	$\leq 95$ mmHg and decrease from baseline $\geq 20$ mmHg $\geq 160$ mmHg and increase from baseline $\geq 20$ mmHg	To be applied for all positions (including missing) except STANDING.

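### SAP 5.8.2 and the table it cites define a treatment-emergent laboratory PCSV differently; if normal means within laboratory range, the text counts only a subset of the table's cases

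*SAP*

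**What the plan says.** SAP Section 5.8.2 calls a laboratory PCSV treatment-emergent when it is "a laboratory value that was normal at Screening and Baseline but became abnormal and met PCSV criteria after treatment with study drug". The next sentence reads "Definition of PCSV is listed in Appendix 11.2".

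Table 5 in that appendix is itself titled as the criteria for treatment-emergent PCSVs and carries its own baseline conditions, row by row. For male hemoglobin the low criterion is "≤115 g/L and > 115 g/L at baseline for male", so the baseline only has to be on the safe side of the same cut-off. A separate hemoglobin criterion is "Decrease from Baseline ≥20 g/L", with no condition on the starting level.

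On missing data, SAP Section 6.3 says "If patients have a missing baseline value, they are grouped in the category" that combines normal with missing. The protocol's laboratory paragraph in Section 10.4.4.2 states: "Number and percentage of patients with a PCSV at any post-randomization time point will be summarized for each clinical laboratory test".

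**The concern.** One SAP table would be produced under two definitions. The sentence in 5.8.2 asks for a normal value at two visits before treatment and an abnormal one afterwards, in addition to the PCSV criterion. Table 5 asks for less. Two programmers working from the same SAP could deliver different PCSV counts.

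What is at stake is the absolute rate in the PCSV summary and which patients appear in the PCSV listing. The patients affected are those who start treatment mildly out of range and then worsen. The summary also carries more weight in SAP version 2.0, because the change table in Section 1.2.4.2 justifies dropping the laboratory shift tables by saying that the PCSV analysis is enough.

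**Working it through.** There is no planned figure to reproduce here; the check compares two rules.

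**Inputs.** Text rule: SAP 5.8.2. Table rule: SAP Appendix 11.2, Table 5. Sampling times: Protocol Table 1 and SAP Table 3. Assumption: normal means within the laboratory range. The SAP does not define the word. However, 5.8.2 lists becoming abnormal and meeting PCSV criteria as separate conditions, and the same section says "Listings are to be provided with flags indicating the out of laboratory range values".

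**The conditions side by side.**

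| Criterion | Table 5 baseline condition | Extra conditions in 5.8.2 |
|---|---|---|
| ALT, AST, by level | at or below 3, 5, 10 or 20 ULN | in range at screening and baseline |
| Alkaline phosphatase | at or below 1.5 ULN | same |
| Hyperkalemia | below 5.5 mmol/L | same |
| Male hemoglobin, low | above 115 g/L | same |
| Hemoglobin fall of at least 20 g/L | none on level | same, and the later value must be abnormal |
| Creatinine percent change | none on level | same, and the later value must be abnormal |
| hs-CRP | none | same, but there is no screening sample |

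**ALT cases in multiples of ULN**, with the text rule coded as screening at most 1, baseline at most 1, later value above 1, and Table 5 met.

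| Screening / baseline / later | Table 5 | 5.8.2 text |
|---|---|---|
| 0.8 / 0.8 / 4 | counted | counted |
| 0.8 / 1.2 / 4 | counted | not counted |
| 1.2 / 0.8 / 4 | counted | not counted |
| 1.5 / 1.5 / 12 | counted | not counted |
| 2.5 / 2.5 / 6 | counted | not counted |
| 3.2 / 3.2 / 4 | not counted | not counted |

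Over a grid of screening, baseline and later ALT values, no combination was counted by the text and missed by Table 5. This follows from the structure, since the text rule is the Table 5 criterion with conditions added. It can only give the same count or a lower one.

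**Which rule the rest of the SAP fits.** With an in-range baseline, a condition such as baseline at or below 20 ULN is always met, so the graded ALT and AST limits would do nothing under the text rule. They have a function only if patients raised at entry can count. The pooled normal-or-missing label in Section 6.3 likewise implies a contrasting group with abnormal baselines.

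**Whether such patients can enrol.** The numbered eligibility criteria set no numerical ALT or AST limit, and diabetes is excluded only when HbA1c exceeds 9.0% (Protocol 6.2.2, criterion 17). Out-of-range entry values are therefore possible. How common they are is not stated.

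**Size, as illustration only.** Let f be the share out of range at screening or baseline and RR their relative PCSV risk. The share of Table 5 cases lost is f x RR / (1 - f + f x RR). All inputs below are assumed, including a 2% PCSV risk in the others and 80 patients per arm.

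- f = 5%, RR = 1: 0.05 / 1.00 = 5%.
- f = 10%, RR = 3: text rule 80 x 0.9 x 0.02 = 1.44 patients; cases lost 80 x 0.1 x 0.06 = 0.48; Table 5 total 1.92; loss 0.48 / 1.92 = 25%.
- f = 30%, RR = 5: 1.50 / 2.20 = 68%.

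At RR = 1 the formula returns f itself, so the spread mostly reflects what was put in. In the middle case the difference is about half a patient per arm.

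**The case against.** The strongest reply is that 5.8.2 sends the reader straight to Appendix 11.2, so the specific table governs and the sentence before it is a loose gloss. If normal only meant not already meeting the PCSV criterion, the two rules would nearly agree. This is a reasonable guess at intent, and it is why the undercount is conditional. It does not remove the conflict. The SAP never says so, the screening condition would remain, and Appendix 11.2 describes its criteria as a reference to be settled before database lock.

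A reader might also infer more than the documents support:

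- *That PCSV rates are biased downward by a known percentage.* No document gives the share out of range at entry, the relative risk or a PCSV rate.
- *That the comparison between arms is distorted.* The same rule applies to all randomized arms, no laboratory hypothesis test is planned, and nothing in the documents points to a differential effect.
- *That these patients would disappear from the report.* Section 5.8.2 keeps change-from-baseline summaries by visit, change plots for all analytes, plots of mean observed values for key analytes including ALT and AST, and flagged listings. Section 4.5.1 requires medically relevant laboratory abnormalities to be recorded as adverse events. The shift tables that were dropped had only been optional.
- *That the text breaks a protocol definition.* The protocol counts PCSVs after randomization without requiring normal entry values, but it does not define treatment emergence, and Section 10.4.4 leaves the thresholds to the sponsor by final SAP approval.

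**Conclusion.** The inconsistency is certain: 5.8.2 and Table 5 state different conditions for the same laboratory summary and listing, and the SAP does not say which prevails. The direction is also certain if normal means within the laboratory range. The text then counts a strict subset of the Table 5 cases, and the patients it drops remain in the safety-set denominator. For hs-CRP the text rule cannot be applied as written.

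The size cannot be determined from the documents. The 5% to 68% range above shows only how strongly it depends on assumed inputs, and the expected counts per arm are small. The effect is on absolute PCSV rates, not demonstrably on differences between arms, and other laboratory outputs limit the harm. It should still be corrected, because the PCSV table is the laboratory summary that version 2.0 relies on in place of shift tables.

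**What to change.** In 5.8.2, strike the conditions about being normal at screening and baseline and about becoming abnormal. State that a treatment-emergent laboratory PCSV is a value after the first dose of study drug that meets the criterion for that analyte in Table 5, including that row's own baseline condition where one is given, with missing baselines handled as in Section 6.3.

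The sentence should not add a general requirement that the baseline did not meet the criterion. That would place a baseline condition on hs-CRP, where Table 5 has none, and remove cases that the table counts.

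The cost is one sentence and one derivation in the programming, with no new data. Version 2.0 was written after the week-12 results were known, so the choice and its reason should be recorded before the final database lock. If a PCSV table was already produced at week 12, the report should say which rule it used.
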